9.1.2 Categorical outcomes

Binary data over time will be analyzed using a Cochran Mantel Haenszel (CMH) test stratified by presence of current major depressive episode. Participants with missing data will be analyzed as though they are non-responders. This will be reported for each endpoint. Differences in proportions along with two-sided 95% CIs will also be reported. Two-sided p-values for the test of no difference between the treatment groups will be provided.

These endpoints will include:

- Proportion of participants with a CGI-I score of “much improved” or “very much improved”.
- Proportion of participants with a $\geq 50\%$ improvement from baseline in Total CAPS-5 score.

10. SAFETY AND TOLERABILITY ANALYSIS

The safety analysis will be run on the Safety population. The analysis of safety assessments in this study will include summaries of the following safety and tolerability data collected for each participant:

- Adverse Events

- Clinical Laboratory Investigations
- C-SSRS
- Vital Signs
- Visual Examinations of Oral Cavity
- BDI-II

Summaries of continuous parameters will include raw values and change from baseline, as appropriate. Listings of safety data will also be presented.

10.1 Adverse Events

All AEs, newly-emergent adverse events (NEAEs), and SAEs will be coded using MedDRA, version 19.0.

Newly emergent adverse events (NEAEs) are defined as any new AE that started after the patient's first dose of P303 study drug, or any unresolved AE first reported in P301 that exhibited an increase in severity, frequency or relationship after the patient's participation in P303 had begun.

An AE summary table will be presented for the following:

- NEAEs by severity
- NEAEs leading to study drug discontinuation
- NEAEs by relationship
- SAEs
- Oral Cavity NEAEs
- All AEs (including both NEAEs and ongoing AEs from the lead-in study)
- All Oral Cavity AEs (including both Oral Cavity NEAEs and ongoing Oral Cavity AEs from the lead-in study)

Summaries of incidence rates (frequencies and percentages) of individual AEs by MedDRA SOC and preferred term will be prepared. Such summaries will be displayed for all NEAEs, NEAEs by maximum severity, NEAEs by strongest relationship to study drug, oral cavity NEAEs, all AEs (including both NEAEs and ongoing AEs from the lead-in study), and all oral cavity AEs (including both oral cavity NEAEs and ongoing oral cavity NEAEs from the lead-in study).

Each participant will be counted only once within each summation level (SOC; preferred term). If a participant experiences more than one NEAE within each summation level only, the NEAE with the strongest relationship or the maximum severity, as appropriate, will be included in the summaries of relationship and severity.

Additionally, a summary of the Oral Cavity AE characteristics will be presented; this includes information such as temporal proximity to the dose, duration and whether the AE was present the following morning.

Adverse events of special interest pertaining to abuse potential will be analyzed separately by treatment group, SOC and preferred term, and displayed in tabular format. Terms to be included may be found in [Appendix 3](#).

In the AE data listings, all AEs will be displayed. A separate by-patient listing of oral cavity AEs (including oral cavity AEs that were ongoing from P301) will be provided. AEs that are newly-emergent will be flagged in all AE listings.

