9.1.2. Screening Overview

The first study visit, Visit 1, will be where the study is explained to the prospective study patient, where written informed consent will be obtained and documented, and where protocol-specified study procedures and assessments will be completed. This visit date is intended to be the same date as the final primary outcome endpoint of the lead-in study (Week 12); however, if there are extenuating circumstances, Visit 1 of P303 may occur within fourteen days of completion of the lead-in study without repeating baseline assessments. If more than fourteen days elapse between the final visit of the lead-in study and start of the P303 study, baseline assessments will need to be repeated.

Once the patient has provided written informed consent to participate and has met all relevant inclusion criteria, this patient is eligible to begin the open-label treatment period starting at bedtime. The patient should be dispensed two bottles of TNX-102 SL tablets, along with instructions on usage. The end-of-study information collected in the double-blind lead-in study will be considered the baseline values for Study P303.

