9.1.4. Visit 1 Baseline Assessments/Procedures (Week 0)

The following assessments/procedures will be completed at Visit 1. If assessments were collected as part of the final visit for the double-blind lead-in study, they will not need to be repeated.

- Obtain written informed consent to participate
- Inclusion criteria

- Review and transcribe new concomitant medications as well as those which are to be continued from the final visit of the double-blind lead-in study
- Review and transcribe new AEs as well as those which are ongoing from the final visit of the double-blind lead-in study
- Review findings obtained at the final visit of the double-blind lead-in study, including visual exam of the oral cavity, vital signs, and weight. The height collected at baseline from the lead-in study will be utilized for BMI calculations in this study.
- Review results of the Beck Depression Inventory (BDI-II) and Columbia-Suicide Severity Rating Scale (C-SSRS) completed at the final visit of the double-blind lead-in study.
- Review all clinical laboratory test results obtained at the final visit of the double-blind lead-in study within 7 days of their release from the central lab (serum chemistries, hematology). Confirm negative urine pregnancy test (for women of child-bearing potential) obtained at the final visit of the double-blind lead-in study.
- Review patient's lifetime psychiatric treatment history, demographic information and medical history to ensure the information recorded during the double-blind lead-in study is accurate and complete, as it will also be included in the extension study's database.
- The following assessments were completed as part of the final visit of the double-blind lead-in study: CAPS-5, PROMIS, and SDS.

Only those patients meeting all of the inclusion criteria will be eligible to continue. After all study requirements for Visit 1 of P303 have been fulfilled, the patient will:

- Be dispensed two bottles of TNX-102 SL tablets and be instructed to begin dosing with study medication at bedtime, starting the evening of Visit 1;
- Receive instruction regarding proper sublingual dosing technique and the time of expected dosing; and
- Schedule the telephone visit 2 and receive an appointment to return to the clinic for Visit 3.

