11. DEFINITIONS, RECORDING, AND REPORTING OF ADVERSE EVENTS AND PREGNANCY

11.1. Definition of Adverse Events

According to International Conference on Harmonisation (ICH) guidance E2A, Clinical Safety Data Management: Definitions and Standards for Expedited Reporting, an adverse event (AE) is any untoward medical occurrence in a patient or clinical investigation patient administered a pharmaceutical product and which is not necessarily required to have a causal relationship with this treatment. An AE can therefore be any unfavorable and unintended sign (including an abnormal laboratory finding, for example), symptom, or disease temporally associated with the use of a medicinal product, whether or not considered related to the medicinal product.

A newly-emergent adverse event (NEAE) is defined as any new AE that starts after the patient's baseline visit for P303, or any ongoing AE that was first reported during the lead-in study and which then exhibits an increase in severity, frequency or relationship after the patient's participation in P303 has begun. NEAEs and "All AEs" will be tallied by SOCs and preferred terms. Adverse events that are ongoing at the time of the patient's baseline visit for P303 but which resolve, or persist without change in severity, frequency or relationship to study drug during the extension study, will be included in the tally of All AEs.

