8.6 Hepatic Impairment

The use of AMRIX is not recommended in patients with mild, moderate or severe hepatic impairment. [See *Warnings and Precautions* (5.4) and *Clinical Pharmacology* (12.3)]

9 DRUG ABUSE AND DEPENDENCE**9.3 Dependence**

Pharmacologic similarities among the tricyclic drugs require that certain withdrawal symptoms be considered when AMRIX is administered, even though they have not been reported to occur with this drug. Abrupt cessation of treatment after prolonged administration rarely may produce nausea, headache, and malaise. These are not indicative of addiction.

AMRIX® (cyclobenzaprine hydrochloride extended-release capsules)**10 OVERDOSAGE**

Although rare, deaths may occur from overdosage with AMRIX. Multiple drug ingestion (including alcohol) is common in deliberate cyclobenzaprine overdose. As management of overdose is complex and changing, it is recommended that the physician contact a poison control center for current information on treatment. Signs and symptoms of toxicity may develop rapidly after cyclobenzaprine overdose; therefore, hospital monitoring is required as soon as possible.

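### SAP 10.1 excludes from newly emergent AEs an event that starts between the final lead-in visit and the first P303 dose and worsens on drug, and the protocol gives two other rules

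*SAP*

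**What the plan says.** SAP 10.1 gives two routes to NEAE status. The first is "any new AE that started after the patient's first dose of P303 study drug". The second follows directly: "or any unresolved AE first reported in P301 that exhibited an increase in severity, frequency or relationship" after participation in P303 began. The same section describes one further table as "All AEs (including both NEAEs and ongoing AEs from the lead-in study", with a parallel table for oral cavity events.

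The protocol defines the same term twice, and differently each time:

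- The synopsis (Safety Analyses) treats as NEAEs the events reported after TNX-102 SL is started in the extension, and also those that worsen after entry. It does not require that a worsening event was first reported in the lead-in study.
- Section 11.1 says a "newly-emergent adverse event (NEAE) is defined as any new AE that starts after" the P303 baseline visit. For worsening, it admits only ongoing events first reported during the lead-in study.

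On timing, Protocol 9.1.2 intends Visit 1 to fall on the date of the lead-in Week 12 visit. In extenuating circumstances, "Visit 1 of P303 may occur within fourteen days of completion of the lead-in study without repeating baseline assessments". A longer delay is allowed if baseline assessments are repeated, and no upper limit is stated. Dosing begins at bedtime on the day of Visit 1 (Protocol 9.1.4). AEs are collected from P303 consent (Protocol 10.3.1), and at Visit 1 the site must "Review and transcribe new AEs as well as those which are ongoing from the final visit of the double-blind lead-in study".

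**The concern.** The protocol expects some AEs to be new at Visit 1, which means they were neither ongoing from the lead-in study nor begun on P303 drug. The SAP definition has no place for such an event if it later worsens. Worsening of a pre-existing condition on treatment is what the second NEAE condition exists to catch, but that condition is tied to where the event was first reported, when the relevant question is whether onset preceded the first dose.

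Safety is the primary objective, and the severity, relationship, oral cavity and discontinuation summaries are built on NEAEs. In those tables the error can only lower the count. Three definitions of one term also leave the programmer to choose, and the choice changes how these events are classified.

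**Working it through.** The plan states no figure to reproduce. The check is to take each pattern of onset and course and apply each written rule to it.

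| Onset and course | SAP 10.1 NEAE | Protocol 11.1 NEAE | Synopsis NEAE | SAP All AEs |
|---|---|---|---|---|
| A. During P301, worsens in P303 | yes | yes | yes, on its natural reading | yes |
| B. During P301, unchanged | no | no | no | yes |
| C. After the final lead-in visit, before Visit 1; worsens on drug | **no** | **no** | yes | not clearly |
| D. After Visit 1, before the first dose; worsens on drug | **no** | yes | yes | not clearly |
| E. After the first P303 dose | yes | yes | yes | yes |

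**Row C.** Onset precedes the first dose, so the SAP's first condition fails. The event was not first reported in P301, so the second fails. Protocol 11.1 fails in the same way: onset precedes the baseline visit, and the event is not from the lead-in study. Only the synopsis counts it.

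**Row D.** The SAP fails for the same two reasons. Protocol 11.1 counts the event because its clock starts at the baseline visit and not at the first dose.

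**All AEs.** The SAP names two components, NEAEs and ongoing lead-in AEs. Rows C and D belong to neither. Protocol 11.1 admits AEs ongoing at the P303 baseline visit to this tally whatever their origin, but names only those that resolve or persist unchanged.

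**Where a row C or D event goes.**

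- Absent: NEAEs by severity, by relationship, oral cavity NEAEs, and NEAEs leading to discontinuation (SAP 10.1 and 10.1.1).
- Present: the AE listing, without the NEAE flag; the listing of AEs leading to discontinuation, if relevant; and the SAE table, if serious (SAP 10.1.2).
- Not excluded by wording: the abuse-potential table and the oral cavity characteristics summary, neither of which is limited to NEAEs.

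**Length of the interval.** With same-day entry it runs from the final lead-in visit to bedtime that day, and only AEs starting in those hours are affected. With delayed entry it is up to 14 days, or longer with repeated baselines.

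**Size.** Neither document gives a sample size or the share of patients entering late, so the count cannot be derived. As an illustration for delayed entry (row C), with every input assumed: 200 patients, 5–20% entering late, 5–10% of those with a new AE in the interval, and 10–20% of those AEs worsening on drug.

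- Low: 200 × 0.05 × 0.05 × 0.10 = 0.05 patients
- High: 200 × 0.20 × 0.10 × 0.20 = 0.8 patients

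Without the last factor the range is 0.5 to 4 patients. That range counts everyone with a new AE in the interval, including those whose AE does not worsen and who are rightly not NEAEs.

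**The case against.** The strongest reply is that the gap may not exist in practice. If the lead-in study continued to collect AEs after its final visit, an interval event would have been first reported in P301 and the SAP's second condition would cover it. The lead-in rules are not in these documents, so this cannot be excluded. Against it, Protocol 9.1.4 lists new AEs separately from ongoing lead-in AEs, which suggests that P303 records at least some of them as its own.

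The second reply is that few patients are affected. This stands. Same-day entry is the intention and delay is the exception, so a reader should not infer that gaps of up to 14 days are routine.

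A reader might also infer that these events are counted in no summary table. The documents do not support that. The All AEs description says *including*, which need not be exhaustive, and the SAE, abuse-potential and oral cavity characteristics summaries are not restricted to NEAEs. The firm statement is limited to the NEAE tables.

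Finally, a reader might infer bias between prior-treatment groups, because patients previously on TNX-102 SL are without P303 drug during any delay and the label in Protocol Appendix 3 (section 9.3) says "Abrupt cessation of treatment after prolonged administration rarely may produce nausea, headache, and malaise". This is weak. The same label section says withdrawal symptoms have not been reported with this drug, and symptoms of stopping would not obviously worsen when drug is resumed, as the gap in the definition requires.

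**Conclusion.** The concern holds in a limited form. As written, SAP 10.1 leaves out of the NEAE tables an AE that begins between the final lead-in visit and the first P303 dose and worsens on drug, provided that the event is recorded in P303 and not through lead-in follow-up. Its inclusion in All AEs is unclear, not ruled out.

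The synopsis, Protocol 11.1 and SAP 10.1 give three different rules, and SAP section 12 declares only the change in study-day numbering. That inconsistency stands whatever the lead-in follow-up rules turn out to be.

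The number of patients is probably very small and, on the assumed inputs for delayed entry, below one. The point merits correction because the rule misclassifies events in the primary safety output, always towards a lower NEAE count, and exact wording repairs it. The documents do not support a claim of material bias in the safety results or of a difference between prior-treatment groups.

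**What to change.** 1. In SAP 10.1, keep the first condition (onset after the first P303 dose) and replace the second with: *any AE with onset before the first P303 dose, whether during P301 or between the final P301 visit and that dose, that increased in severity, frequency or relationship after the first P303 dose*. This makes the first dose the anchor for both onset and worsening.
2. Define All AEs as NEAEs plus every AE ongoing at the first P303 dose, whatever its origin. Apply the same definition to All Oral Cavity AEs.
3. Bring the synopsis and Protocol 11.1 into line with this definition. If the protocol is not to be amended, declare the SAP definition in SAP section 12 as a change from the planned analysis.

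The cost is a few sentences of editing. No new data are needed, since onset date and time are already collected (Protocol 10.3.1). A protocol change would need ethics committee or IRB approval (Protocol 13.1), which the SAP section 12 route avoids. The NEAE count may rise slightly.

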10.1.1 Adverse Events Leading to Discontinuation of Study Drug

A summary of incidence rates (frequencies and percentages) of NEAEs leading to discontinuation of study drug by treatment group, SOC, and preferred term will be prepared for the Safety population.

A data listing of AEs leading to discontinuation of study drug will also be provided, displaying details of the event(s) captured on the CRF.

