Safety data will be summarized by treatment group. Adverse events will be coded using the same version of the Medical Dictionary for Regulatory Activities (MedDRA) as used for the lead-in study and will be summarized overall and by preferred term and system organ class (SOC). Adverse events will also be summarized by severity and relationship to study drug. Serious AEs and AEs leading to discontinuation of study drug will also be summarized. Adverse events that are ongoing at Week 12 from the lead-in study will be transcribed into the eCRF. All other adverse events that are reported after starting TNX-102 SL 5.6 mg in this extension study, or that worsen after entry into the extension study, will be considered newly emergent AEs (NEAEs), even if the type of event was previously reported (and resolved) during the lead-in study.

Actual values and changes from both baselines for clinical laboratory test results, vital sign measurements, and in the BDI-II score will be summarized at endpoint using descriptive statistics (n, mean, SD, median, minimum, and maximum). The number of patients with baseline and treatment-emergent suicidal ideation and/or suicidal behavior or self-injurious behavior, based on the C-SSRS, will be summarized by treatment group.

Efficacy Analyses:

Descriptive statistics by treatment group and study visit will be displayed for a number of efficacy endpoints, including:

- Change from both baselines in the total CAPS-5 score
- Proportion of patients with a CGI-I score of “very much improved” or “much improved” from both baselines
- Change from both baselines in the SDS total score
- Change from both baselines in the individual items assessed using the SDS
- Change from both baselines in patients’ quality of sleep using the PROMIS Sleep Disturbance scale
- Change from both baselines in CAPS-5 symptom cluster subscores
- Proportion of patients with a $\geq 50\%$ improvement from baseline (both baselines) in total CAPS-5 score
- Change from both baselines in BDI-II score

Hypothesis testing will also be performed on the above efficacy endpoints. Missing values will not be imputed, and no adjustments will be made for multiplicity.

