12.1. Evaluation of Safety

Safety will be assessed by the monitoring and recording of AEs, clinical laboratory tests, vital signs, visual examination of the oral cavity findings, the monitoring of suicidality using the Columbia C-SSRS scale, and patient-rated assessments of depressive symptomology (BDI-II).

Adverse events will be coded using the Medical Dictionary for Regulatory Activities (MedDRA) and will be summarized overall and by preferred term and system organ class. Adverse events will also be summarized by severity and relationship to study drug. Serious AEs and AEs leading to discontinuation of study drug will also be summarized.

Actual values and changes from the extension study baseline values for clinical laboratory test results and vital sign measurements will be summarized at endpoint using descriptive statistics (n, mean, standard deviation (SD), median, minimum, and maximum). Laboratory values will be displayed in the data listings along with corresponding normal ranges, and those that are outside the normal range will be flagged.

Based on the C-SSRS results, the frequency and severity of suicidal ideation and behavior will be tabulated at each time point. The number of patients with baseline and treatment-emergent suicidal ideation and/or suicidal behavior or self-injurious behavior, based on the C-SSRS, will be summarized by treatment group.

All data gathered will be listed by patient and parameter, and clinically significant abnormalities should be recorded as AEs.

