8. STUDY PARTICIPANTS AND DEMOGRAPHICS

8.1 Disposition of Participants and Withdrawals

The numbers and percentage of participants entering, completing the study, and withdrawing from the study, along with reasons for withdrawal, will be tabulated overall and by treatment group. This summary will be based on all participants who have data entered into the database.

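### The SAP's discontinuation tables count only newly emergent AEs, so stopping P303 drug for an unchanged lead-in AE is not shown as a discontinuation event in any table

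*SAP*

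**What the plan says.** Protocol 12.1 states: "Serious AEs and AEs leading to discontinuation of study drug will also be summarized". The synopsis has the same commitment, and neither place limits it to NEAEs.

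The SAP limits both of its discontinuation tabulations. The overview table in SAP 10.1 has a row for "NEAEs leading to study drug discontinuation". SAP 10.1.1 then plans "A summary of incidence rates (frequencies and percentages) of NEAEs leading to discontinuation of study drug by treatment group, SOC, and preferred term".

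An AE that began in the lead-in is an NEAE only if it worsens. SAP 10.1 admits "any unresolved AE first reported in P301 that exhibited an increase in severity, frequency or relationship". Protocol 11.1 says where the rest go: ongoing AEs that "persist without change in severity, frequency or relationship to study drug during the extension study, will be included in the tally of All AEs".

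Three other provisions bear on the point:

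- Lead-in AEs still open at rollover are in the P303 database. The synopsis says: "Adverse events that are ongoing at Week 12 from the lead-in study will be transcribed into the eCRF".
- The listing is not limited to NEAEs. SAP 10.1.1 says: "A data listing of AEs leading to discontinuation of study drug will also be provided".
- SAP 8.1 covers disposition, with participants "withdrawing from the study, along with reasons for withdrawal, will be tabulated overall and by treatment group".

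SAP 12, on changes from the planned analysis, declares only the Day 0/Day 1 convention.

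**The concern.** Safety is the primary objective, and discontinuation because of an AE is one of its central tolerability results. An emergent-event filter normally removes conditions that were present before any exposure to the drug. In this extension it can remove drug effects as well, because patients randomised to TNX-102 SL in the lead-in have already had 12 weeks of active drug when P303 begins.

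Take a patient who has continuous sedation on TNX-102 SL in the lead-in, rolls over, and later stops because it has not gone away. Nothing about the event has increased, so it is not an NEAE and drops out of the discontinuation tables. The two lead-in treatment groups are the columns of those tables. The TNX/TNX column is the only one with up to about 24 weeks of continuous exposure (Protocol 6.1), and its tolerability could look slightly better than it was.

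**Working it through.** The documents give no discontinuation count or rate, so there is no planned figure to reproduce. The check traces one event through every planned output that could count it: an AE that began in the lead-in, did not change, and led the patient to stop P303 drug.

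| Planned output | Is the event counted? | Is it shown as a discontinuation? |
|---|---|---|
| Discontinuation row of the overview table (SAP 10.1) | No, NEAEs only | No |
| Discontinuation table by SOC and preferred term (SAP 10.1.1) | No, NEAEs only | No |
| All AEs row and SOC/preferred-term table (SAP 10.1) | Yes | No, not split by discontinuation |
| SAE table (SAP 10.1.2) | Only if serious; no NEAE limit | No |
| Listing of AEs leading to discontinuation (SAP 10.1.1) | Yes | Yes, but a listing gives no rates |
| Disposition table (SAP 8.1) | Only if the patient also leaves the study with an AE as the recorded reason | Study withdrawal only, without the event term |

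No row is a table that both counts the event and identifies it as the one that led to discontinuation.

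**Direction by group, for side effects of the drug**

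- Placebo/TNX: the first dose of active drug is in P303, so a drug-caused AE must begin in P303. It is an NEAE and is counted.
- TNX/TNX: a drug-caused AE may have begun in the lead-in. If it continues unchanged, it is not counted.

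AEs that are not caused by the drug can be carried over in either group, including AEs that began on placebo.

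**Size**

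Let s be the share of AE discontinuations that are due to unchanged lead-in AEs. Then:

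tabulated rate = true rate × (1 − s)

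Since s cannot be negative, the error is downward or zero. The documents do not give s. With an assumed true rate of 5%:

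- s = 0: 5% × 1.00 = 5.0%
- s = 10%: 5% × 0.90 = 4.5%
- s = 25%: 5% × 0.75 = 3.75%
- s = 50%: 5% × 0.50 = 2.5%

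In patients, suppose that 10% to 30% of 100 TNX/TNX patients enter with an ongoing AE and that 3% to 8% of those stop for it unchanged. The omitted number is then between 100 × 0.10 × 0.03 = 0.3 and 100 × 0.30 × 0.08 = 2.4. Every input in this size section is an assumption.

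**The case against.** The strongest reply has four parts.

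**The event is not lost.** It is in the All AEs incidence table and in the discontinuation listing. NEAEs are flagged in the AE listings, so the others can be picked out, and disposition may count the patient. This stands. A reader might infer that such events appear in no incidence table at all, and the SAP does not support that. What is missing is the attribution to discontinuation by group and term.

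**The SAP may only be interpreting general wording.** Protocol 12 leaves the complete description of the analyses to the SAP. Protocol 12.1 also mentions AEs by severity and relationship without qualification, and the SAP uses NEAEs there too. This weakens the charge of a contradiction but does not remove the gap. The SAP does not filter SAEs, which share the protocol's sentence with discontinuations. It also adds all-event rows for AEs overall and for oral cavity AEs, but none for discontinuations.

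**The category is narrow.** Entrants completed the lead-in, had at least 60% compliance and chose to continue (Protocol 7.2), which selects against stopping for an AE already tolerated. An increase in frequency or relationship makes a lead-in AE an NEAE. Under the synopsis, so does recurrence after resolution. Oral numbness that clears between doses may therefore be counted; the problem needs an event recorded as continuous and unchanged. This stands, and it is why the number is probably small.

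**Size and imbalance are not documented.** This also stands. A reader might divide the 0.3 to 2.4 omitted patients by an assumed 5 true discontinuations and report an understatement of 6% to 48%. All of those inputs are chosen, and the upper end multiplies two upper limits over a small denominator. Nor must the AE and disposition tables disagree. They may, but one counts stopping drug and the other leaving the study, so a difference could also have another cause.

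**Conclusion.** The point holds as a gap in one planned summary. Both SAP discontinuation tabulations are narrower than the protocol's commitment, and the change is not declared. That much rests on the text alone.

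The direction follows from the definitions: the tables can miss AE discontinuations and cannot add any. For drug-caused AEs the loss can fall only on the TNX/TNX group. That is an inference from the design, and it does not extend to AEs that began on placebo. The documents do not support a claim of a large or measured bias between the groups. The number of patients is probably small and may be zero, although with few discontinuations a single omission would be visible in the rate. The change is worth making because it costs little and concerns the primary objective.

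**What to change.** In SAP 10.1 and 10.1.1, count every AE whose recorded action was discontinuation of P303 study drug, whenever it began. Present the result by treatment group, SOC and preferred term, with two sub-rows:

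- NEAEs
- AEs ongoing unchanged from the lead-in

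This keeps the NEAE view that the SAP already plans. Under the table, explain any difference from the number withdrawn for an AE in the disposition table (SAP 8.1). If the NEAE restriction is kept instead, SAP 12 should declare and justify it.

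The cost is a change of SAP wording and one extra table shell. Ongoing lead-in AEs are already to be transcribed into the eCRF and the full listing is already planned, so no new data are needed. The reported discontinuation rate may rise slightly.
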